Patients will be identified by reviewing the emergency department (ED), or any UNC Hospitals Medical Service in EPIC. We will review each patient's EPIC ED/hospital encounter to see if they meet inclusion criteria.

Research coordinators will begin screening for eligible patients that come through the ED, or any UNC Hospitals Medical Service. If a patient is consented and enrolled, study drug administration could begin while the patient is still in the ED. However, depending on the patient's status once they are discharged from the ED, patients may go to the ICU or to a floor bed. Therefore, study drug administration could be given on the floor or in the ICU. The admitting diagnosis will determine where a patient will go once discharged from the ED. Therefore we could possibly be conducting this study in any of our adult ICUs or any of our floor beds.

Version: 02-09-2018

Informed Consent:

Informed consent will be obtained from each patient or surrogate before enrollment in the trial. No study procedures will be conducted before obtaining informed consent. For surrogates that are not present during the screening period of a patient that is not at decision-making capacity, we will contact by phone to obtain verbal consent.

Randomization:

After informed consent is given, a study coordinator will contact the investigational drug service pharmacy and inform them about enrollment and about the stratification. An assignment will be made by a randomization table to administer either treprostinil therapy or placebo. The paper system will be structured to maintain 2:1 active drug to placebo randomization. Randomization will be stratified by trauma and non-trauma diagnosis since the pathophysiology and outcomes of acute lung injury in trauma patients are different than for other etiologies.

Justification for Placebo:

There is currently no approved PGI₂ agent for the prevention of ARDS. The need for a placebo arm in this study is necessary to compare the difference in PaO₂/FiO₂ ratios from patients that receive treprostinil.

[figure not shown]
Minorities and Women:

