Analysis of covariance (ANCOVA) will be used to compare trends for the primary outcome PaO₂/FiO₂ ratio between days 0 and 7 between intervention and control patients. PaO₂/FiO₂ ratio is measured at baseline (day 0), and days 2, 7,. The difference in treatment groups for change from baseline to day 7 and days 2 will be estimated using an ANCOVA adjusting for baseline value. 95% and 80% confidence intervals for the difference in least squares means will be calculated. Due to small sample sizes, substantial normality departures due to skewness will be assessed. As a supportive exploratory analysis, if a number of patients do not have a day 7 assessment, a mixed linear model for repeated measures (MMRM) of PaO₂/FiO₂ ratio at days 0, 2, and 7 will be explored. The focus of the analysis is to assess preliminary evidence of efficacy. Sample size permitting, trends will be evaluated separately in trauma and non-trauma patients.

The secondary efficacy outcome, 28 day ventilator free days, is defined as days alive and free of mechanical ventilation during the first 28 days after randomization. Patients who die will receive 0 ventilator free days. Patients who are discharged free of mechanical ventilation prior to day 28 will be assumed to remain free of mechanical ventilation unless they are readmitted. Ventilator free days is expected to be skewed. Comparisons between treatment groups will focus on 95% and 80% confidence intervals of the Hodges-Lehman estimator for location shift.

Time until mechanical ventilation and time until death will be described via Kaplan-Meier survival curves.

Remaining efficacy outcomes and biomarkers will be analyzed with similar methods. Categorical outcomes will be characterized by odds ratios and assessed with chi-squared tests or Fisher's exact tests. Biomarker values change from baseline will be assessed comparing treatment groups overall and stratified by whether the acute lung injury was resolved by day 28.

Sample size calculation

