Sample size calculations are based on simple t tests. Assuming a change in PaO_2/FiO_2 ratio of 15 in the intervention group and 10 in controls, a standard deviation of 6 (effect size of 0.833), and power of 0.80, the study would require 34 patients in the intervention group and 17 patients in the control group for a 2-sided test with significance level p < 0.05. While we will not approach these numbers, they serve to provide a framework as to the sample size needed to observe clinically meaningful changes in oxygenation as statistically significant. This current proposal centers on safety and feasibility, and thus does not meet the statistical criteria needed to observe minimally significant changes in oxygenation. The planned sample size of 30 total participants has 80% power to produce a 2-sided 80% confidence interval with lower confidence limit above 0 if the true effect size is 0.833.

Twenty-eight day ventilator-free days is a continuous variable. The mean 28 day ventilator free

Version: 02-09-2018

days for the control group of the most recent ARDS network trial was 15 days (95% CI 14.1 – 15.9). The patients enrolled for this trial will have significantly more ventilator free days as a number of them will not require mechanical ventilation at all. A study with 100 patients would have a power of 0.8 to show a 3 day difference in 28 day ventilator free days assuming a value of 22 for controls and 25 for intervention patients, with a SD of 5 days. Since this is an initial, smaller feasibility and proof of concept trial, we will not be able to obtain this level of statistical rigor.

Study feasibility will be assessed by enrollment rate over the first 6 months of the study. If the enrollment rate at that time suggests high feasibility such that the enrollment target of 30 patients can be exceeded easily within the funded enrollment period, we will consider amending the protocol to enroll a small number of additional subjects. This will be discussed and reviewed by the study DSMB. [name], Department of Biostatistics, UNC will provide statistical support.

Part 3. Data Collection and Site Monitoring

Data Collection

Research coordinators will collect data and enter it directly into a computer-based data entry system managed by the TRACS institute or on paper data forms.

Site Monitoring

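### Cheap, minor improvement: carry the trauma stratum into the ANCOVA and mixed model under one fixed rule, and keep biomarker contrasts by Day-28 resolution descriptive

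*Combined protocol and SAP*

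**What the plan says.** The Randomization section makes trauma a design factor and gives the reason: "Randomization will be stratified by trauma and non-trauma diagnosis since the pathophysiology and outcomes of acute lung injury in trauma patients are different". Allocation is 2:1, and no block size is stated.

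Under Statistical Considerations/Data Analysis, Efficacy, the difference in PaO2/FiO2 change to Day 2 and Day 7 "will be estimated using an ANCOVA adjusting for baseline value", reported with 95% and 80% confidence intervals. No other covariate is named. A mixed model is held in reserve: "As a supportive exploratory analysis, if a number of patients do not have a day 7 assessment". It names no covariates. Trauma returns only as a subgroup look: "Sample size permitting, trends will be evaluated separately in trauma and non-trauma patients".

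The same section plans biomarker comparisons "comparing treatment groups overall and stratified by whether the acute lung injury was resolved by day 28". Resolution is not defined there.

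Under Sample size calculation, "Sample size calculations are based on simple t tests", and 30 patients are said to give "80% power to produce a 2-sided 80% confidence interval with lower confidence limit above 0" at a true effect size of 0.833.

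**The concern.** The plan states its own belief that trauma matters to outcome, balances on it, and then leaves it out of the model that gives the overall estimate. A separate look by stratum does not enter that estimate or its interval. If trauma predicts PaO2/FiO2 change after baseline adjustment, its variance stays in the residual and the interval is wider than it need be. In a 30-patient trial whose efficacy output is two confidence intervals, width is what the reader will use.

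The biomarker split is a separate matter. Biomarker change runs from Day 0 to Day 7, while resolution is settled by Day 28. The Hypothesis section expects treatment to improve oxygenation and ventilation outcomes, so treatment may change who counts as resolved. Arms compared within a resolution group are then no longer protected by randomisation, and a difference could appear or vanish through selection. The definition is also open. A Day-28 radiographic Lung Injury Score is scheduled (Reference Measurements; Appendix 2), but the Efficacy text does not tie it to resolution, and patients discharged earlier are described only as receiving a phone assessment.

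**Working it through.** **1. The plan's own figure.** Inputs from Sample size calculation: changes of 15 and 10, SD 6, so effect 5/6 = 0.833; 30 patients at 2:1, so 20 and 10. The noncentrality is 0.833/√(1/20 + 1/10) on 28 df. The chance that a two-sided 80% interval lies above 0 is 0.799 (noncentral t) or 0.808 (normal). The stated 80% reproduces.

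**2. Width with 30 analysed.** Assumed, because the documents do not say: k trauma patients, and a gap g between trauma and non-trauma in mean change after baseline adjustment, in residual SDs. If 2:1 holds exactly within strata, the ratio of interval width, stratum omitted over adjusted, is approximately

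√(1 + 30·p(1−p)·g²/27) ÷ 1.00097, with p = k/30,

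where 1.00097 is the 80% t quantile on 26 df over that on 27 df. For k = 6:
- g = 0.5: √(1 + 1.2/27) ÷ 1.00097 = 1.021
- g = 1: √(1 + 4.8/27) ÷ 1.00097 = 1.084

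Simulation with blocks of 3 within stratum (40,000 trials per cell) agrees closely:

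| Trauma patients | g = 0 | 0.25 | 0.5 | 1 |
|---|---|---|---|---|
| 3 | 0.999 | 1.002 | 1.011 | 1.046 |
| 6 | 0.999 | 1.004 | 1.020 | 1.081 |
| 9 | 0.999 | 1.006 | 1.027 | 1.106 |
| 15 | 0.999 | 1.007 | 1.032 | 1.125 |

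These counts are multiples of the assumed block, so they build in exact balance and show the lowest cost. With 4 or 5 trauma patients, adjusting costs about 0.4-0.5% at no gap. With 3 trauma patients and blocks of 6 it costs about 1%. Over all these cases:
- no gap: adjusting costs 0.1-1.1%
- 0.25 SD: from about 0.9% wider to 0.7% narrower when adjusted
- 0.5 SD: about 0-3% wider when omitted
- 1 SD: about 3-12% wider when omitted

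**3. Validity.** With no true effect, the chance of an 80% interval above 0 (nominal 0.10) was 0.078-0.102 omitted and 0.096-0.102 adjusted. Coverage of the 80% interval with 6 trauma patients and g = 1 was 0.832 omitted and 0.799 adjusted. Omission is conservative.

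**4. Chance of an 80% interval above 0 at effect 0.833, omitted v adjusted.** This depends on whether SD 6 is the total SD, the natural reading of a simple t test, or the SD within strata.

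| Case | SD 6 total | SD 6 within strata |
|---|---|---|
| 6 trauma, g = 0.5 | 0.790 v 0.799 | 0.777 v 0.785 |
| 6 trauma, g = 1 | 0.808 v 0.835 | 0.756 v 0.788 |
| 15 trauma, g = 1 | 0.810 v 0.851 | 0.736 v 0.789 |

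**5. Day 7.** Appendix 2 takes PaO2/FiO2 only from patients still in hospital. Suppose 15 of 30 remain, lost at random (an assumption). When the term is kept, adjusting costs about 1-2.4% at no gap, breaks even near 0.5 SD, and gains about 7-10% at 1 SD. A rule requiring at least 3 patients and both arms in the smaller stratum keeps the term in about 12% of trials with 3 trauma patients randomised, 59% with 6, 86% with 9 and 96% with 15.

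**6. Biomarkers by resolution.** Simulated with no drug effect on the biomarker, with severity driving both biomarker change (loading 0.3 or 0.6) and resolution. The spurious within-group difference is:
- 0 if resolution is equal in the arms
- 0.02-0.09 SD at 60% v 50% resolved
- 0.03-0.16 SD at 67% v 50%
- 0.06-0.35 SD at 82% v 50%

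The sampling error is larger. At 82% v 50% of 20 and 10, the resolved groups are 16.4 and 5, giving SE √(1/16.4 + 1/5) = 0.51 SD. The unresolved groups are 3.6 and 5, giving √(1/3.6 + 1/5) = 0.69 SD.

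**The case against.** The best case for leaving the plan alone is that nothing in it is invalid. The estimate is unbiased, the interval errs on the safe side, and the trial presents itself as a feasibility and safety study seeking preliminary evidence. The gain rests on assumptions: the plan says that outcomes differ in trauma, not that PaO2/FiO2 change differs after baseline adjustment. Trauma patients may be few, since candidates are found by "reviewing the emergency department (ED), or any UNC Hospitals Medical Service in EPIC". Adjusting is not free either, least of all at Day 7, one of the two primary time points. All of this stands, and it is why the point is minor.

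It does not remove the point. The possible gain exceeds the possible cost with 30 analysed, and the plan itself supplies the reason to expect a gap.

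On biomarkers, the overall comparison is already planned and no decision hangs on the split. That also stands. What remains is that nothing limits the split to description.

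A reader might infer more: that omitting a stratification factor biases the result, inflates false positives, or pulls the trial below its stated 80%. The documents do not support this. Balance within strata protects the estimate, and with SD 6 read as the total SD the baseline-only model still gives 0.785-0.810 in every cell examined. The 80% figure is in any case a power statement, not a decision rule.

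**Conclusion.** The point holds as a cheap improvement of minor weight: possible lost precision, not a fault of validity or sample size. With 30 analysed, the trade is at most about 1% of width lost if trauma is irrelevant, against about 0-3% gained at a 0.5 SD gap and 3-12% at 1 SD. The top of that range needs half the patients to be trauma cases, which is extreme given where screening takes place. At Day 7 with heavy loss there is a net gain only above about 0.5 SD. Trauma share, gap, block size and Day 7 losses are all assumed.

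The biomarker contrasts within resolution groups cannot carry a between-arm inference. A reader might conclude that the whole biomarker analysis is compromised; it is not, because the overall comparison is randomised, and the likely bias within groups is smaller than sampling noise at this size.

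**What to change.** Add trauma/non-trauma as a fixed effect in the ANCOVA and the mixed model. Before unblinding, fix one rule that gives Day 2, Day 7 and the mixed model the same covariates. For example: keep the term only if, among patients analysed at Day 7, the smaller stratum has at least 3 patients and both arms; otherwise adjust for baseline only throughout. A rule applied separately at each time point would not do. It cannot be used in a single mixed model, and it could put the two primary contrasts on different models. If trauma patients are few, the term will usually be dropped.

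Make the overall, baseline-adjusted biomarker comparison the only between-arm inference, and label the split by resolution descriptive. Define resolution before unblinding: whether the Day-28 Lung Injury Score is used, and how early discharges and deaths before Day 28 are classed.

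The cost is a few sentences in the analysis plan, no new data, and one degree of freedom when the term is kept.

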- 3) To assess the effect of treprostinil inhalation on oxygenation in patients with acute hypoxic respiratory failure with, or at risk for, development of ARDS
- 4) To assess the effect of treprostinil inhalation on various biomarkers thought to be related to the pathogenesis and/or clinical course of ARDS.

We propose a proof of concept, double blinded, placebo controlled study of inhaled treprostinil for patients with "at-risk" or early ARDS. Early, or pre-ARDS will be defined as acute hypoxemia and unilateral pulmonary infiltrates in patients presenting with conditions that are conducive to ARDS (e.g. pneumonia, sepsis, aspiration, trauma) but do not yet meet criteria for ARDS: require mechanical ventilation, bilateral infiltrates on CXR, and PaO_2/FiO_2 ratio < 300. The primary outcome will be PaO_2/FiO_2 ratio. We will also measure other physiologic and clinical outcomes and levels of inflammatory and pro-fibrotic biomarkers. This exploratory initial study will enroll 30 patients to assess feasibility and safety in this population.

Hypothesis:

- 1. Treprostinil inhalation is safe at planned dose titration in patients with acute hypoxemic respiratory failure
- 2. Treprostinil will improve oxygenation and other secondary outcomes related to mechanical ventilation initiation and duration, as well as exhibit effects on ARDS-related pro-inflammatory and pro-fibrotic biomarkers.

Study Design:

- 1) Single Center, proof of concept, 2:1 active drug to placebo controlled, double-blinded
- 2) Target of 30 patients enrolled
- 3) Patients will be randomized to receive either treprostinil or saline inhalation placebo
- 4) Patients will be followed to hospital discharge or day 28, whichever comes first. Those discharged prior to day 28 will be assumed free of mechanical ventilation and alive unless readmitted in that period. This will be confirmed by phone.

Sample Size/Interim Monitoring:

1) This is primarily a feasibility, safety and proof of concept trial.

Version: 02-09-2018

- 2) The primary endpoint is Change in PaO₂/FiO₂ ratio from Study Day 0 to 2, 7
- 3) Trial progress will be monitored by an independent Data and Safety Monitoring Board to determine if the study should stop for safety reasons. The first interim review will occur6 months following enrollment of the first patient or after the first 15 patients (which-ever occurs first) have been enrolled.

Inclusion Criteria:

- 1) Adults age 18-80 years.

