- 14) Imminent need for intubation or non-invasive ventilation (patients that are requiring non-invasive ventilation soley for Obstructive Sleep Apnea are not excluded) (A high flow nasal cannula flow rate greater than 50LPM will be considered as an imminent need for positive pressure as well.)
- 15) Patient has comfort care orders written or otherwise will not receive supplemental oxygen including High Flow Nasal Cannula Oxygen Patient is Do Not Resuscitate/Do Not Intubate
- 16) Patient has a tracheotomy
- 17) Patient is currently receiving prostacyclin therapy [Epoprostenol (Flolan or Veltri) Iloprost (Ventavis) Treprostinil (Orenitram, oral) (Remodulin, IV or SC)]
- 18) Patient has a language barrier
- 19) Patient is unable to complete the breathing maneuver

Rationale for Exclusions:

Patients less than 18 years old are excluded because of limited clinical trial data with treprostinil in subjects younger than 18 years. Criteria 4, 8, 9, 13, 14 exclude patients unlikely to survive to the primary study endpoint or whose underlying condition or ventilator management complicates

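### Ventilator-free days pile up at the maximum of 28, so the planned Hodges-Lehmann intervals can report a shift of 0 when the gain is real; add tie-valid summaries beside them

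*Combined protocol and SAP*

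**What the plan says.** Under Statistical Considerations/Data Analysis, Efficacy, VFD counts days alive and off mechanical ventilation in the first 28 days, and deaths score 0. The section expects skewness and then states: "Comparisons between treatment groups will focus on 95% and 80% confidence intervals of the Hodges-Lehman estimator for location shift". It mentions neither ties nor the maximum of 28.

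The Sample size calculation section says "Twenty-eight day ventilator-free days is a continuous variable". It cites an ARDS network control-group mean of 15 days and expects that this trial's patients "will have significantly more ventilator free days as a number of them will not require mechanical ventilation at all". Its power statement for 100 patients is based on "assuming a value of 22 for controls and 25 for intervention patients, with a SD of 5 days".

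Three features push patients to 28:
- The Exclusion Criteria rule out "Imminent need for intubation or non-invasive ventilation".
- Study Design says "Those discharged prior to day 28 will be assumed free of mechanical ventilation and alive unless readmitted in that period".
- Study Stopping Rules describes the population as not yet needing a ventilator.

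For the PaO2/FiO2 endpoint only, the Sample size calculation section says that 30 patients give "80% power to produce a 2-sided 80% confidence interval with lower confidence limit above 0".

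**The concern.** HL estimates the amount by which one distribution is shifted relative to the other. That suits a continuous outcome with room to move. Here the likely benefit is that more patients reach 28, and nobody can go beyond it. A placebo patient at 28 can be tied but never beaten. Enough such patients hold the lower limit, and eventually the estimate, at 0 or below, even if every treprostinil patient does as well as the scale allows. A reader who sees a shift of 0 may take it as no effect.

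**Working it through.** **Inputs.** Target of 30 patients at 2:1, so 20:10 (Study Design). HL intervals at 80% and 95% (Efficacy). Means 22 and 25, SD 5 (Sample size calculation). VFD range 0 to 28 (Efficacy).

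**The plan's own figures reproduce.** For VFD at 2:1, placebo n = (1.960 + 0.842)² × 5² × 1.5 / 3² = 32.7, so 33 + 66 = 99; with 100 patients the power is 0.807. For PaO2/FiO2 with 30 patients and effect size 0.833, the power for an 80% interval above 0 is 0.808 (normal) or 0.799 (t). The plan gives no figure for the HL interval.

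**Exact threshold.** The HL interval takes its limits from the 20 × 10 = 200 ordered treprostinil-minus-placebo differences. From the exact rank-sum distribution, the lower limit is the 71st smallest for 80% (actual coverage 80.2%) and the 56th for 95% (95.1%). Each placebo patient at 28 makes 20 differences 0 or less.
- 4 at 28: 80 differences ≤ 0, and 80 ≥ 71, so the 80% limit cannot exceed 0. With 3 it can (60 < 71).
- 3 at 28: 60 ≥ 56, so the 95% limit cannot exceed 0.
- 6 at 28: 120 of 200 are ≤ 0, so the estimate itself cannot be positive.

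Best case with 4 placebo patients at 28, the other 6 at 0 and all 20 treprostinil patients at 28: the 80% lower limit is exactly 0, although the Wilcoxon p is 0.00016. Inverting the tie-corrected test just above 0 gives z = 1.06, below the 1.282 needed; the exact permutation one-sided p is 0.111, above 0.10. Tie correction does move the 95% threshold from 3 to 4. For other splits, the 80%/95% thresholds are 4/4 at 19:11, 4/3 at 21:9, 5/4 at 18:12 and 3/3 at 22:8.

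**How large can the control share p at 28 be?** With mean 22 and a point mass at 28, the variance between the mass and the rest is 36p/(1 − p). This cannot exceed 25, so p ≤ 25/(25 + 36) = 41%.

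**Chance of 4 or more of 10 placebo patients at 28 (binomial):** 22% at p = 25%, 35% at 30%, 62% at 40%.

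**Simulation at the plan's means and control SD.** Assumptions: no deaths; patients below 28 uniform with mean μ = (22 − 28p)/(1 − p) in both arms, width set so that the control SD is 5.0; whole days; treprostinil share at 28 = (25 − μ)/(28 − μ), which gives SD 4.6; 20,000 trials of 20:10.

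| Controls / treprostinil at 28 | HL exactly 0 | HL 80% CI above 0 | HL 95% CI above 0 |
|---|---|---|---|
| 25 / 62% | 21% | 36% | 17% |
| 30 / 65% | 29% | 28% | 12% |
| 35 / 68% | 39% | 20% | 8% |
| 40 / 70% | 52% | 13% | 5% |

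On the same data the Welch interval lies above 0 in about 59% (80% CI) and 29 to 31% (95% CI). With unrounded days the HL 80% rates are about 38/30/22/17%. With no effect, the HL 80% interval lies above 0 in 1.5 to 5% and Welch in about 10%, which is the nominal rate, so Welch's advantage is not bought with false positives.

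**The case against.** **The same gain is analysed elsewhere.** In these scenarios the whole benefit is avoided ventilation. Intubation is its own secondary endpoint, with an odds ratio planned, and time to ventilation gets Kaplan-Meier curves. An 80% interval for that odds ratio favours treprostinil in 60 to 74% of the simulated trials, at least as often as Welch. This stands and limits the harm, although the plan names no interval level for odds ratios. If the benefit were mainly shorter ventilation, the order changes: in three such cases the odds ratio succeeded in 16 to 34%, HL in 37 to 48% and Welch in 65 to 69%.

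**No success rule is breached.** A reader might infer that VFD fails the plan's own criterion. The documents do not support that: a lower limit above 0 is stated only for PaO2/FiO2, and for VFD the plan disclaims adequate power.

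**The intervals are not blocked.** A reader might infer that they are unusable. They can be computed and can show harm; only a showing of benefit is ruled out, and only once enough placebo patients score 28. At shares of 25 to 30% that is the minority case. The documents also leave open whether BiPAP or CPAP counts as mechanical ventilation for VFD; if it does, fewer patients reach 28.

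**Deaths are left out of the simulation.** This stands too. With 5 to 15% of controls and 3 to 8% of treprostinil patients dying, Welch succeeds in 27 to 42% and HL in 1 to 16%. Those cases exceed the plan's SD of 5. The gap remains, but the 59% should not be taken as a forecast.

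**HL is a defensible robust choice.** Making the mean the lead summary would change the estimand, which is debatable. The algebra does not require HL to be dropped.

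**Conclusion.** The point holds as a minor one. The thresholds of 4 of 10 (80%) and 3 of 10 (95%) are exact for a 20:10 split and the standard ordered-difference interval. How often they bite depends on an assumed share at 28, at most 41% of controls at the plan's mean and SD. The consequence is that a real VFD gain may be reported as a shift of 0 on one secondary endpoint. No sample size or stopping rule uses this interval. A reader might also infer that a larger trial would inherit the problem, but the documents commit no later trial to this summary.

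**What to change.** In the Efficacy section, keep the HL intervals and add:
- the win probability P(treprostinil > placebo) + 0.5 P(tie), with 80% and 95% Brunner-Munzel intervals on the logit scale;
- the difference in mean VFD with Welch 80% and 95% intervals, which matches the means and SD in the Sample size calculation section;
- the number of patients per arm at 0 and at 28;
- a sentence saying that an HL shift of 0 is not to be read as no effect.

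In the Sample size calculation section, replace the description of VFD as continuous: it is bounded at 0 and 28, with ties expected.

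The cost is some wording, a few lines of code and slightly more reporting, on data already collected. The mean is sensitive to the rule that deaths score 0. Welch intervals are approximate with 10 placebo patients (coverage 80 to 81% and 94 to 95% in the death-free scenarios above). The win probability is not in days, and its interval is slightly conservative (83 to 84% and 96 to 97%).

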The following parameters will be measured and recorded using values closest in time to Dose 1 study drug administration on days 0-11 (depending on the specific variable), or until stopping of study drug, whichever comes first. All vascular pressures will be zero-referenced to the mid-axillary line with the patient supine.

- 1) Fluid intake and output (Twenty-four hour net fluid balance)
- 2) Vital signs: Heart rate, systolic and diastolic blood pressure, body temperature, CVP
- 3) Modified Brussels Score data days 0-14:
 - a) Vasopressor use (Y/N), worst systolic BP, creatinine, bilirubin, and platelet count for the day.
- 4) Presence of myopathy
- 5) Frontal Chest Radiograph Lung Injury Score (Days 0, 3, 7 and 28)
- 6) Concomitant medications, including nebulized and inhaled medications.
- 7) Blood banked for future analyses
- 8) Biomarker samples. Plasma obtained from two, 6 ml EDTA anti-coagulated blood samples will be divided immediately after centrifugation into 12 equal 1 ml aliquots in specified tubes and frozen at –80°C. Samples will be temporarily stored in the Pulmonary Division Lab space freezers in Burnett Womack Building or in the Emergency Room freezer. Specimens will be stored in the Koury Oral Health Sciences Building. Reference biomarker list above (Days 0, 3, and 7).

Statistical Considerations/Data Analysis:

Safety

Safety will be assessed via percentage of patients and number of events recorded for the following outcomes:

- Adverse events, serious adverse events, unanticipated problems, study discontinuation overall and due to adverse event, and deaths.
- Cases of dose intolerance, including cases of worsening oxygenation, intractable cough, and systemic hypotension following dosing
- Cases of intubation or noninvasive ventilation for worsening hypoxemia

Percentages of all outcomes above will be provided to the DSMB for regular unblinded review of safety, to be assessed every 6 months or after 15 participants have completed the 28 day trial or been discharged from the hospital (whichever occurs first).

Efficacy

Version: 02-09-2018

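### Sparse binary outcomes and the safety outcomes need risk differences with intervals: at about 20 versus 10 patients the planned odds ratio can degenerate, and the safety percentages carry no measure of precision

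*Combined protocol and SAP*

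**What the plan says.** The Efficacy part of Statistical Considerations/Data Analysis gives one sentence to binary outcomes: "Categorical outcomes will be characterized by odds ratios and assessed with chi-squared tests" or Fisher's exact tests. It states no interval for the odds ratio, no handling of a zero cell and no rule for choosing the test. Among the Secondary Endpoints it covers intubation and mechanical ventilation, need for BiPAP/CPAP or high-flow oxygen above 50 LPM, 28-day mortality and hospital mortality. The same part does specify 95% and 80% confidence intervals for the PaO₂/FiO₂ difference and for the ventilator-free-day shift.

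The Safety part says: "Safety will be assessed via percentage of patients and number of events recorded for the following outcomes". The list covers adverse events, discontinuations, deaths, dose intolerance, and intubation or noninvasive ventilation. No interval is mentioned.

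Study Design sets the size, "Target of 30 patients enrolled", and the Randomization section the ratio: "The paper system will be structured to maintain 2:1 active drug to placebo randomization". The split of about 20 treprostinil and 10 placebo follows from these two; it is not stated as such.

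**The concern.** An odds ratio is a poor main summary when a cell of the 2×2 table is empty. With no event in the control arm it is infinite, with none in the active arm it is 0, and with none in either it is undefined. In each case the log odds ratio and its Wald interval do not exist. A control arm of about 10 patients makes this a practical matter for any uncommon outcome.

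Safety is a main purpose of this trial, yet a percentage alone does not show how little a small count rules out. A reader of the results would have intervals for oxygenation and ventilator-free days, but none for the results that bear on whether to go on to a larger trial.

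**Working it through.** **Inputs.** N = 30 (Study Design); 2:1 allocation (Randomization), taken as exactly 20:10. Ventilator-free-day planning values: means 22 and 25, SD 5 (Sample size calculation). Deaths score 0 ventilator-free days (Efficacy). ARDS 28-day mortality of about 45% in general ICUs (Study Stopping Rules). The documents give no rate of intubation, noninvasive ventilation or death for the enrolled population, so other rates are shown as a range. Arms are independent binomials with no missing data.

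**The plan's own figures.** It gives none for binary outcomes. Its PaO₂/FiO₂ figures reproduce by the normal approximation. Control n = 1.5 × (1.960 + 0.842)² × 6²/5² = 16.95, so 17 and 34 as stated. For 20:10 and an 80% interval, 5/[6√(1/20 + 1/10)] − 1.282 = 0.870, a power of 81% (79.9% by noncentral t) against the stated 80%.

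**Chance of an arm with no events.** With the same rate p in both arms, a = (1−p)¹⁰ for control, b = (1−p)²⁰ for active, and P(at least one) = a + b − ab.

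| p | control zero | active zero | at least one |
|---|---|---|---|
| 5% | 60% | 36% | 74% |
| 10% | 35% | 12% | 43% |
| 15% | 20% | 4% | 23% |
| 20% | 11% | 1% | 12% |
| 45% | 0.25% | <0.01% | 0.25% |

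The chance passes one half only when p is below about 8.7%. At p = 10% the 43% divides into an infinite odds ratio (31%), an odds ratio of 0 (8%) and an undefined one (4%).

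**Death, from the plan's assumptions.** A variable with mean m and standard deviation s takes the value 0 with probability at most s²/(s² + m²) (Cantelli's inequality). Control: 25/(25 + 484) = 4.9%. Active: 25/(25 + 625) = 3.8%. Everyone who dies scores 0, so these cap 28-day mortality. At the caps, P(no deaths) is (1 − 0.0491)¹⁰ = 60% in control and (1 − 0.0385)²⁰ = 46% in active. Then P(at least one arm with none) = 0.604 + 0.456 − 0.276 = 78%. Lower mortality raises it.

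**Ventilation or death, from the same assumptions.** Ventilator-free days cannot exceed 28. A mean of 22 therefore needs at least 6/28 = 21.4% of controls, and a mean of 25 at least 3/28 = 10.7% of active patients, to be ventilated or die. P(control zero) ≤ 0.786¹⁰ = 9.0% and P(active zero) ≤ 0.893²⁰ = 10.4%, so P(at least one) ≤ 0.090 + 0.104 − 0.009 = 18%.

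**What can be reported in such tables.**

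| active vs control | odds ratio (exact 95% CI) | risk difference in points, Newcombe 95% CI; 80% CI |
|---|---|---|
| 0/20 vs 2/10 | 0 (0 to 2.56) | −20: −51 to +2; −40 to −6 |
| 3/20 vs 0/10 | infinite (0.21 to infinity) | +15: −14 to +36; −1 to +28 |
| 0/20 vs 0/10 | undefined | 0: −28 to +16; −14 to +8 |

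**Safety precision.** With 0 events in n, the two-sided 95% Clopper-Pearson upper limit is 1 − 0.025^(1/n): 16.8% for n = 20 and 30.8% for n = 10.

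**Choice of test.** For 0/20 versus 2/10, uncorrected chi-squared is 30 × (0×8 − 20×2)²/(20×10×2×28) = 4.29, p = 0.038. Fisher gives 45/435, p = 0.103. Enumeration of all 21 × 11 tables at nominal 0.05 (the plan states no level for these tests) gives a maximum true size of 5.2% for uncorrected chi-squared and 3.3% for Fisher. At p = 5% the sizes are 3.1% and 0.5%.

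**The case against.** The strongest reply is that these are secondary, exploratory outcomes in a trial that openly disclaims statistical rigor, and that odds ratios with chi-squared or Fisher tests are conventional. Much of it stands.

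- A reader might infer that a zero arm is likely for every binary outcome. The documents do not support that. They give no rate for intubation or noninvasive ventilation, and their ventilator-free-day means hold the chance to about 18% for ventilation-or-death. At 45% mortality it would be 0.25%, though that figure describes ARDS in general ICUs, while this trial enrols patients not yet ventilated. Common drug effects such as cough (54% in Risk Assessment) will rarely be absent from an arm.
- A reader might infer that no estimate or interval survives. An odds ratio of 0 is finite, and when only one arm is empty the exact interval keeps one informative bound. Only the table with no event in either arm leaves nothing.
- A reader might infer that the open test choice inflates error. At nominal 0.05 neither test materially exceeds 5%, and the plan proposes no categorical test at any looser level. The usual rule that all expected counts be at least 5 is met only when exactly 15 of 30 patients have the event, so an analyst following it would almost always use Fisher. The plan does not state that rule, nor whether chi-squared would be continuity-corrected.
- Safety is not left without any comparison between arms. Intubation, noninvasive ventilation and death are also secondary endpoints, ventilation and death get Kaplan-Meier curves, and the DSMB sees data by group. Nothing in the plan says that an absence of events would be read as proof of safety.

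The reply leaves open that the planned summary degenerates in sparse tables, that the odds ratio has no interval method, and that the Safety part plans no measure of precision.

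**Conclusion.** The point holds as a low-severity improvement of method. For uncommon outcomes at about 20:10 the odds ratio is an unreliable main summary. The case is clearest for mortality, with at least a 78% chance of an arm without deaths if the plan's ventilator-free-day means and SD are right. Those values were set for a hypothetical 100-patient comparison, and a larger SD would loosen the mortality cap and lower the 78%. For ventilation-or-death the risk is at most about 18%. For the other binary outcomes it depends on rates that the documents do not give. The absence of intervals for safety needs no rate assumption: 0 of 20 is compatible with a true rate of 16.8%. The open test choice is a missing detail and not an error-rate problem. All figures assume exactly 20:10 and complete follow-up.

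**What to change.** In the Efficacy part, for intubation, noninvasive ventilation, 28-day mortality and hospital mortality, make the main summary the counts per arm and the risk difference with Newcombe or Miettinen-Nurminen 80% and 95% intervals. These match the intervals already planned for PaO₂/FiO₂ and ventilator-free days and stay finite with empty cells. The odds ratio may be kept as an optional addition; if so, state its interval method and what is reported when a cell is zero. Name one test in advance, or none.

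In the Safety part, add an exact or score interval per arm and the same between-arm difference for the main listed outcomes.

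The cost is a few sentences of SAP wording and a little extra output from standard software. The intervals will be wide, which is a fair picture of what 30 patients can show.
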